### **3.2. RANDOMIZATION AND MASKING**

This is a non-randomized, open-label study.

### **3.3. HANDLING OF DATA**

#### **3.3.1. Strata and Covariates**

No stratifications among subjects or the use of covariates is planned.

### **3.3.2. Examination of Subject Subsets**

No subgroup analyses are planned.

### **3.3.3. Multiple Testing and Comparisons**

No adjustments for multiplicity are planned.

### **3.3.4. Missing Data and Outliers**

Every effort was made to obtain required data at each scheduled evaluation from all subjects. In situations where it was not possible to obtain all data, imputations of missing data may be necessary. These situations are described below. Unless otherwise specified, no imputation for missing data will be performed.

### **3.3.5. Imputation of Incomplete Dates**

#### **3.3.5.1. Imputation of Adverse Events and Prior/Concomitant Medications and Procedures**

An incomplete date occurs when the exact date an event started or ended cannot be obtained from a subject. The database contains data fields for month, day, and year. A date is incomplete if at least one of these three fields is not known.

For many of the planned analyses, a complete date is necessary to determine if the event should be included in the analysis (i.e., if the event is treatment-emergent) or to establish the duration of an event. In such cases, incomplete dates will be imputed.

For the purposes of handling partially reported start and stop dates for an event the following algorithm will be applied:

- Missing start day, but month and year present:

If the event occurs in the same month and year as the dosing of study drug, then the start day of the event will be assigned to the day of first dose of study drug.

Otherwise, the start day will be set to the first day of the month.

- Missing start day and month, but year present:

If an event occurs in the same year as study drug dosing, then the start date of the event will be assigned to Day 1.

Otherwise, the start day and month will be set to 01 January.

- Missing all components of a start date:

Assign the date of Day 1.

- Missing end day, but month and year present:

The day will be set to the last day of the month.

- Missing end day and month, but year present:

The end day and month will be set to the date of study completion/discontinuation. However, if the study completion/discontinuation year is greater than the year of the event, then the day and month will be set to 31 December.

- In the event of a completely missing end date (year not present and ongoing not checked), the end date will be imputed as the last day of dosing. If the imputed date is later than the date of study completion/discontinuation, then the date of study completion/discontinuation will be imputed for the date.

If any imputed date causes the end date to occur prior to the start date of the event, the start date of the event will be used for the imputation of the end date. If any imputed date causes the start date of the event to occur after the end date of the event, the end date of the event will be used for the imputation of the start date. In subject data listings, start and stop date of events will be displayed as reported on the eCRF (i.e., imputed values will not be listed).

### **3.3.5.2. Imputation of Missing Date of Initial Cancer Diagnosis**

For any partial initial diagnosis dates, the following imputation rules will be applied:

- Missing day will be set to 01.
- If both month and day are missing, the date will be set to 01 January.

### **3.3.5.3. Imputation of Missing Date of Death**

Partial death dates are not expected. However, for any partial death dates, the following imputation rules will be applied:

- Missing day will be set to 01.
- If both month and day are missing, the date will be set to 01 January.

### **3.3.6. Imputation of Missing Severity or Relationship for Adverse Events**

Adverse events (AEs) with missing severity or relationship to study drug will not be imputed. Actual values will be presented in the data listings.

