### 7.1.1 *Intensity and Causality of Adverse Events*

The event's **relationship to the study drug or treatment procedure** should be indicated according to the following definitions:

|                    |   |
|--------------------|---|
| Related     | The adverse event is related to the treatment or procedure. An adverse event (AE) is considered related if there is "a reasonable possibility" that the AE may have been caused by the study drug (i.e., there are facts, evidence, or arguments to suggest possible causation). |
| Not Related | The adverse event is clearly not related to the treatment or procedure.  |

The **frequency** of the event should be indicated according to the following definitions:

|                       |  |
|-----------------------|--|
| Single episode | This is the first and only experience/episode of the event in the trial. |
| Recurrent      | The event has occurred before in the trial.                              |
| Continuous     | The event is continuing.   |

The **intensity** grade of the event should be indicated according to the following definitions: All intensity of AEs will be assessed by the Investigator using NCI CTCAE v5.0.

The **outcome** should be indicated according to the following definitions:

|                                   |   |
|-----------------------------------|---|
| Recovered without sequelae | Patient recovered completely from the AE.   |
| Recovered with sequelae    | Patient has recovered from the AE but displays other symptoms.  |
| Ongoing                    | Patient continues to exhibit symptoms of the AE. The patient will be followed until the AE is resolved. |
| Death                      | Patient died (the date of death should be entered as the SAE resolution date).                          |
| Unknown                    | Outcome is unknown due to loss to follow-up.  |

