### 5.8.1. Adverse Events

Treatment emergent adverse events (TEAEs) will be coded by System Organ Class and preferred term using MedDRA version 23.0 or higher. The investigator grades the severity/intensity of each AE with National Cancer Institute Common Terminology Criteria for Adverse Events (CTCAE) v5.0 and categorizes the relatedness of the AE to SPH4336.

Summaries that are displayed by system organ class and preferred terms will be ordered by descending incidence of system organ class and preferred term within each system organ class. Summaries of the following types will be presented:

- Overall Summary of Treatment-Emergent Adverse Events;
- Treatment-Emergent Adverse Events by System Organ Class and Preferred Term;
- Related Treatment-Emergent Adverse Events by CTCAE Grade, System Organ Class and Preferred Term;
- CTCAE Grade 3 or Higher Treatment-Emergent Adverse Events by System Organ Class and Preferred Term;
- Serious Treatment-Emergent Adverse Events by System Organ Class and Preferred Term;
- Treatment-Emergent Adverse Events Leading to Death by System Organ Class and Preferred Term;
- Treatment-Emergent Adverse Events Leading to Discontinuation of SPH4336 by System Organ Class and Preferred Term;

Summaries of AEs will include the number and percentages of subjects with each preferred term and SOC unless specified otherwise. Missing onset dates will be imputed as previously outlined in Section 3.3.5.1 as required to determine treatment-emergent events.

All adverse events reported will be listed for individual subjects showing both verbatim and preferred terms. All adverse events that occurred prior to the initiation of study drug or more than 28 days after last dose of study drug will be excluded from the tables, but will be included in the listings. No imputation for missing severity or relationship will be applied for listings.

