## 9. **PROPOSED TABLES, LISTINGS, AND FIGURES**

Number	Title	Population
Tables		
14.1.1	Subject Disposition	Safety
14.1.2	Demographic Characteristics	Safety
14.1.3	Baseline Characteristics and Cancer History	Safety
14.1.4	Medical History	Safety
14.1.5	Prior Therapies and Surgery	Safety
14.1.6	Study Drug Exposure and Compliance	Safety
14.2.1	Best Overall Response	Efficacy
14.3.1.1	Overall Summary of Treatment-Emergent Adverse Events	Safety
14.3.1.2	Treatment-Emergent Adverse Events by System Organ Class and Preferred Term	Safety
14.3.1.3	Related Treatment-Emergent Adverse Events by CTCAE Grade, System Organ Class and Preferred Term	Safety
14.3.1.4	CTCAE Grade 3 or Higher Treatment-Emergent Adverse Events by System Organ Class and Preferred Term	Safety
14.3.1.5	Serious Treatment-Emergent Adverse Events by System Organ Class and Preferred Term	Safety
14.3.1.6	Treatment-Emergent Adverse Events Leading to Death by System Organ Class and Preferred Term	Safety
14.3.1.7	Treatment-Emergent Adverse Events Leading to Discontinuation of SPH4336 by System Organ Class and Preferred Term	Safety
14.3.2.1	Listing of Deaths	Safety
14.3.2.2	Listing of Serious Adverse Events	Safety
14.3.2.3	Listing of Grade 3 or Higher Adverse Events	Safety
14.3.2.4	Listing of Adverse Events Leading to Discontinuation of SPH4336	Safety
14.3.3.1	Hematology Results and Changes from Baseline	Safety
14.3.3.2	Shift in Hematology Laboratory Values in CTCAE Toxicity Grade to the Worst Abnormal Value	Safety
14.3.3.3	Chemistry Results and Changes from Baseline	Safety
14.3.3.4	Shift in Chemistry Laboratory Values in CTCAE Toxicity Grade to the Worst Abnormal Value	Safety
14.3.3.5	Coagulation Results and Changes from Baseline	Safety
14.3.3.6	Shift in Coagulation Laboratory Values in CTCAE Toxicity Grade to the Worst Abnormal Value	Safety

14.3.4.1	Concomitant Medications	Safety
14.3.4.2	Concomitant Procedures	Safety
14.3.5.1	Vital Signs Results and Changes from Baseline	Safety
14.3.5.2	12-Lead Electrocardiogram - Univariate Summary by Parameter and Visit	Safety
14.3.5.3	12-Lead Electrocardiogram Interpretation -- Shift from Baseline to Worst Post-Baseline Value	Safety
14.3.6	Summary of ECOG Performance Status	Safety

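### Adverse events with missing relationship or grade drop out of the related and Grade 3 or higher tables, because the SAP neither imputes them nor provides a Missing category

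*SAP*

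**What the plan says.** SAP 3.3.4 sets the default: "Unless otherwise specified, no imputation for missing data will be performed". SAP 3.3.6 then covers these two fields without limiting the rule to any type of output: "Adverse events (AEs) with missing severity or relationship to study drug will not be imputed". It adds: "Actual values will be presented in the data listings". SAP 5.8.1 (Adverse Events) returns to the subject in narrower terms: "No imputation for missing severity or relationship will be applied for listings".

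Two of the planned summaries select on these fields. Table 14.3.1.3 is titled "Related Treatment-Emergent Adverse Events by CTCAE Grade, System Organ Class and Preferred Term", and Table 14.3.1.4 is titled "CTCAE Grade 3 or Higher Treatment-Emergent Adverse Events by System Organ Class and Preferred Term". No Missing row, worst-case rule or supplementary count is described for either.

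Protocol 7.1.1 has a two-level relationship scale. An event is Related if the drug may reasonably have caused it. It is Not Related if it "is clearly not related" to the treatment or procedure. The protocol does not say what to do when the field is blank.

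**The concern.** Without imputation and without a Missing category, an unassessed event is absent from the related table, just as an event judged Not Related would be. An ungraded event is absent from the Grade 3 or higher table, just as a Grade 1 or 2 event would be. Nothing in either table would tell the reader that this had happened.

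The direction is fixed. Leaving an event out of a count can lower that count or leave it unchanged, but cannot raise it. Severity and relationship of adverse events belong to a secondary endpoint (Protocol 2.2.2). Because the study closed early for futility and efficacy is reduced to limited tabulations (SAP 5.7.2 and 7), the safety tables are most of the quantitative output.

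**Working it through.** The plan states no figure on this point, so there is none to reproduce. The check has three parts.

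**1. Where an affected TEAE appears under the SAP as written**

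| Missing field | All TEAEs (14.3.1.2) | Related, by grade (14.3.1.3) | Grade 3 or higher (14.3.1.4) | AE listing (16.2.7) |
|---|---|---|---|---|
| Relationship only | Yes | No | Yes, if Grade 3 or higher | Yes |
| Grade only, event Related | Yes | No stated place | No | Yes |
| Both | Yes | No | No | Yes |

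The omissions are inferred, but they follow directly: an event with no value cannot meet a selection on that value. Listing 14.3.2.3 also selects on grade, so an ungraded event would be found only in the full listing 16.2.7.

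**2. Comparison with related rules**

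- Protocol 7.1.1: the threshold for Related is low and that for Not Related is high. An unassessed event has not been judged clearly unrelated, yet it is tabulated as if it had been. This comparison bears on relationship only.
- SAP 3.3.5.1 and 3.3.9: a completely missing start date is set to Day 1, and an event starting on Day 1 is taken to follow dosing. Doubt about timing is thus resolved by counting the event as treatment-emergent.
- SAP 5.8.2 (Clinical Laboratory Assessments): where two grades share the same numerical limits, the higher is assigned.

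For dates and tied laboratory grades the SAP resolves doubt towards counting toxicity. For missing relationship and grade the effect is the opposite, and no reason is given.

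**3. Possible size**

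Inputs: 14 patients enrolled (SAP 5.7.2); the denominator is all dosed subjects (SAP 4.1). That all 14 were dosed is an assumption, so N = 13 is also shown. The number k of subjects whose only qualifying event in a given row has a missing value is not in the documents; 1 to 3 is illustrative.

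Change in incidence = 100 × k / N percentage points.

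| k | N = 14 | N = 13 |
|---|---|---|
| 0 | 0 | 0 |
| 1 | 7.1 | 7.7 |
| 2 | 14.3 | 15.4 |
| 3 | 21.4 | 23.1 |

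A subject who has another qualifying event in the same row contributes nothing to k.

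**The case against.** The strongest reply is that little is lost and blanks should be rare. Affected events stay in the all-TEAE table and the full listing. The tables of serious events, deaths and discontinuations do not select on grade or relationship. Laboratory results are graded from the measured values and shown in shift tables, so cytopenias and transaminase rises remain visible by severity even if the adverse event grade is blank. Protocol 12.4 requires missing data to be explained and the investigator to sign each completed eCRF. Protocol 7.2.1 requires relationship and intensity to be documented for serious events. All of this stands, and it keeps the point minor. It does not supply a table rule, and the SAP gives these missing values a section of their own, so it foresees them.

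Four stronger readings are tempting but are not supported:

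- *The SAP contradicts the protocol.* Protocol 7.1.1 tells the investigator how to classify an event and gives no rule for a blank. Leaving a value missing does not assign Not Related, and no planned table carries that label. The tension is in the tabular effect, not in the text.
- *SAP 3.3.6 and 5.8.1 conflict.* The second limits its statement to listings, which may hint at a different rule for tables, but none is given and both statements can be followed together. The wording is loose.
- *Any one such event moves an incidence by 7 points.* It does so only if the subject has no other qualifying event in that row and all 14 patients were dosed.
- *An ungraded event should count as Grade 3 or higher.* Nothing in the documents requires this, and it could turn a minor ungraded event into severe toxicity.

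**Conclusion.** The point holds as a minor one. The SAP states a no-imputation rule and gives affected events no place in the two tables that depend on the missing field, so they are left out without notice. Any error runs towards less related or less severe toxicity. The size is 7.1 percentage points for each subject whose only qualifying event is affected, assuming all 14 enrolled patients were dosed (7.7 if 13 were). The actual effect cannot be derived from the documents and is zero if nothing is missing.

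The argument from Protocol 7.1.1 supports the relationship half only. The severity half rests on how the tables are built and on the SAP's own handling of uncertain dates and tied laboratory grades.

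**What to change.** Add a table rule to SAP 3.3.6, for example:

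*In summary tables, a TEAE with missing relationship is counted as related. A TEAE with missing grade is not assigned a grade: it is shown in a Missing grade row in Table 14.3.1.3 if it is related or counted as related, and reported as a footnoted count in Table 14.3.1.4. Listings show values as reported.*

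Reword the sentence in SAP 5.8.1 (Adverse Events) so that it points to this rule and no longer leaves the handling in tables open.

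The cost is a sentence or two and minor programming. Related rates may look slightly less favourable, and an unrelated event left blank would be counted as related; querying the blanks before database lock limits this. If there are no blanks, no table changes.

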### **3.3.7. Data Handling Rules for Efficacy Data**

Subjects were assigned to one of the following best overall response categories: Complete Response (CR), Partial Response (PR), Stable Disease (SD), Progressive Disease (PD), or Not Evaluable (NE) by the investigator.

Per Response Evaluation Criteria in Solid Tumors (RECIST) v1.1, a subject response was classified as NE for a timepoint if no measurement is performed. If only a subset of lesion measurements are made at an assessment, the case will be considered NE unless the contribution of the individual missing lesion(s) is considered to not change the assigned time point response.

A subject will be considered to have a response if all the criteria for response have been met per RECIST v1.1.

### **3.3.8. Presentations by Study Visit**

Visits will be presented according to the nominal visit obtained from the CRF or laboratory data. Unscheduled assessments will be included in the listings.

### **3.3.9. Definitions and Terminology**

#### Age

The age of a subject is defined as the number of whole years between the subject's birth date and the date of informed consent.

#### Baseline Value

For purposes of analysis, the baseline value is defined as the last non-missing value obtained prior to administration of SPH4336. If the last non-missing collection of ECGs is collected in triplicate, the average will be used for the baseline value.

#### Day 1 (Baseline)

Day 1 is the earliest day that study drug is initiated.

#### Study Day

Study Day is defined relative to the day of first dose administration on Cycle 1, Day 1. Thus, the study day of an event is calculated as:

$$\begin{aligned} & \text{date of event} - \text{date of first dose} + 1, \text{ if event is on or after Cycle 1 Day 1, OR} \\ & \text{date of event} - \text{date of first dose}, \text{ if event is before Cycle 1 Day 1} \end{aligned}$$

There is no Day 0.

#### Days on Study

Days on Study is the number of days from Day 1 to the date of study completion or early termination as recorded on the End of Study CRF.

### Study Visit

Study Visit is the nominal visit as recorded on the CRF.

### Change from Baseline

Change from baseline for a given endpoint is defined as the Study Day X value minus the Baseline Value.

### Last Dose of Study Drug

Last Dose of study drug is defined as the last date that the subject received SPH4336 as determined by last date of dosing as recorded on the End of Treatment CRF.

### Study Drug Exposure

Study drug exposure will be summarized by duration of exposure (days), total dose received (mg) and daily dose (mg) received.

Duration of exposure will be presented in days and is defined as the number of days from the date of First Dose to the date of Last Dose calculated as:

*(the date of last dose – date of first dose + 1)* and corrected for any days dose was held.

Total dose received (mg) will be calculated as the (sum of all tablets dispensed – sum of all tablets returned) x (100 mg) + (sum of all tablets dispensed – sum of all tablets returned) x (200 mg). If the number of tablets dispensed or returned is missing, it is assumed that the number of tablets returned was 0.

Daily dose received (mg) will be calculated as total dose received (mg) / duration of exposure in days for each subject.

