## SPH4336-US-01 PROTOCOL SYNOPSIS

|                                  |   |
|----------------------------------|---|
| Title                            | A Phase 2 Multicenter, Open-Label Study of the CDK4/6 Inhibitor SPH4336 in Subjects with Locally Advanced or Metastatic Liposarcomas  |
| Protocol No.                     | SPH4336-US-01   |
| Phase                            | 2   |
| Sponsor                          | Shanghai Pharma Biotherapeutics USA Inc.  |
| Study location                   | US  |
| Investigational Product          | SPH4336   |
| Study Population                 | Subjects with locally advanced or metastatic CDK4-positive liposarcomas   |
| Primary Objectives [Endpoints]   | 

• Evaluate the efficacy of SPH4336 in subjects with CDK4-positive liposarcomas [PFS at 12 weeks]

  |
| Secondary Objectives [Endpoints] | 

• Evaluate the safety and tolerability profile of SPH4336 [AEs]

• Evaluate the pharmacokinetics of SPH4336 [Non-compartmental PK]

• Median PFS, Best Overall Response, Duration of Response, Time to Response, Overall Survival and other efficacy assessments

• Evaluate tumor tissue biomarkers for activity (e.g., phospho-Rb, Ki-67) in the first 10 patients

 |
| Treatment Regimen                | The dose will be 400 mg QD. SPH4336 tablets will be administered orally each day on a continuous schedule.  |

|                     |  |
|---------------------|--|

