### 6 INVESTIGATIONAL PRODUCT

#### 6.1 Dosage forms

SPH4336 will be provided as film-coated tablets containing 100 or 200 mg SPH4336 free base (30 tablets per soda-lime glass bottle with a high-density polyethylene cap and a sealing gasket for a medicinal glass bottle).

Excipients in the formulation include the following:

- povidone K30
- cellactose® 80
- croscarmellose sodium
- magnesium stearate
- a film coating premix (gastric soluble, Opadry®, model 85G630034-CN, orange)

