### Study Drug Treatment Compliance

Treatment compliance will be calculated as a percentage based on the total dose received (mg) divided by the adjusted planned administration (mg) (extent of exposure after adjusting for any dose modifications or holds).

Adjusted planned administration (mg) will be calculated based on the number of days of planned dose multiplied by 400 (mg). Number of days of planned dose will be defined as the cycle duration or days until end of treatment (whichever was smaller) for each planned dose per cycle minus the number of days dose held as reported on the Study Drug Administration CRF.

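### The SAP's total-dose formula does not separate the two tablet strengths, and its missing-count rule credits every dispensed tablet as taken

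*SAP*

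**What the plan says.** SAP section 3.3.9, under Study Drug Exposure, defines total dose received as the sum of two terms. The first contains "sum of all tablets dispensed – sum of all tablets returned) x (100 mg" and the second "sum of all tablets dispensed – sum of all tablets returned) x (200 mg" (both fragments are cut inside their brackets). The tablet count is worded identically in the two terms, and neither is limited to tablets of its own strength.

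Missing counts are covered by one sentence: "If the number of tablets dispensed or returned is missing, it is assumed that the number of tablets returned was 0". No upper limit is placed on the result.

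Two further measures use this total as numerator:

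- Daily dose: "Daily dose received (mg) will be calculated as total dose received (mg) / duration of exposure in days for each subject".
- Compliance: "Treatment compliance will be calculated as a percentage based on the total dose received (mg) divided by the adjusted planned administration (mg" (closing bracket cut). For its denominator, "Adjusted planned administration (mg) will be calculated based on the number of days of planned dose multiplied by 400 (mg", with held days taken off as reported on the Study Drug Administration CRF.

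In the protocol, the synopsis gives the regimen ("The dose will be 400 mg QD"), and section 6.1 lists tablets of 100 mg and 200 mg, packed as "30 tablets per soda-lime glass bottle". The results go to SAP Table 14.1.6 and Listing 16.2.5.3.

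**The concern.** The formula and the missing-count rule are separate problems that act on the same numerator.

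The formula, programmed as worded, credits each tablet with 100 + 200 = 300 mg whatever its strength. Protocol 10.1 says the SAP prevails where the two documents differ, so the SAP text is what a programmer or a later reader will rely on.

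The missing-count rule replaces an unknown return count with the value that gives the largest possible dose. For that period the measure stops describing what the subject took and describes what was handed out. If the dispensed count is the unknown one, setting returns to zero does not supply it.

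The study was closed for lack of efficacy. A reader of the report will ask whether subjects received the planned dose, and the exposure and compliance table is where they will look. An overstated figure could lead them to dismiss under-dosing too readily as an explanation.

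**Working it through.** The documents state no exposure or compliance result, so there is no plan figure to reproduce. The benchmark is a fully adherent subject over one full cycle.

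**Inputs**

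- Planned dose 400 mg once daily (Protocol synopsis); cycle of 28 days (Protocol 4, SAP 1.1).
- Strengths 100 mg and 200 mg, 30 tablets per bottle (Protocol 6.1).
- Formulas for total dose, daily dose and compliance (SAP 3.3.9).
- Assumptions: the tablet mixes below, and dispensing in whole bottles. The documents give a pack size but no dispensing rule.

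**Benchmark.** 28 × 400 = 11,200 mg, which is 400 mg/day and 100% compliance.

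**Step 1: the formula as worded, all counts known, full adherence.** Total = tablets × 100 + tablets × 200 = tablets × 300.

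| Daily tablets | Tablets in 28 days | Total (mg) | mg/day | Compliance |
|---|---|---|---|---|
| 2 × 200 mg | 56 | 16,800 | 600 | 150% |
| 1 × 200 mg + 2 × 100 mg | 84 | 25,200 | 900 | 225% |
| 4 × 100 mg | 112 | 33,600 | 1,200 | 300% |

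The calculated value would fall below 100% only if true adherence were below 11,200/16,800 = 66.7%, 11,200/25,200 = 44.4% or 11,200/33,600 = 33.3% respectively.

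**Step 2: counts split by strength, all counts known.** Total = (100 mg tablets × 100) + (200 mg tablets × 200). Each mix returns 11,200 mg, 400 mg/day and 100%. The excess in Step 1 therefore comes wholly from the missing strength restriction.

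**Step 3: counts split by strength, return count missing and set to 0.** A 28-day cycle on 200 mg tablets uses 56. In whole bottles that is two, or 60 tablets, so the credited total is 60 × 200 = 12,000 mg.

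- Full cycle: 12,000/11,200 = 107%, and 12,000/28 = 429 mg/day. Actual intake does not enter the calculation, so the result is the same at 100%, 80% or 50% true adherence.
- Stop on Day 21: 12,000/(21 × 400) = 12,000/8,400 = 143%.
- Stop on Day 15: 12,000/(15 × 400) = 12,000/6,000 = 200%, and 800 mg/day.
- Two complete cycles with known returns, then a stop on Day 15 of the third with the return missing: (2 × 11,200 + 12,000)/(71 × 400) = 34,400/28,400 = 121%, and 34,400/71 = 485 mg/day.

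**Step 4: dispensed count missing.** Dispensed minus returned becomes an unknown minus 0, which is undefined. If software drops the missing term from the sum, the period contributes nothing and the total is too low.

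**Step 5: effect on a group mean.** SAP 5.7.2 reports 14 patients enrolled. If all 14 are summarised, one subject at 121% instead of 100% raises mean compliance by 21/14 = 1.5 percentage points.

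**The case against.** The strongest reply is that the formula has one term for each of the two strengths, which makes sense only if each term is meant for its own tablets. Read literally, the two terms would collapse to a single multiplication by 300 mg. This stands: the likeliest explanation is a dropped label, and nothing shows that the literal version was programmed. It explains the error but leaves the wording uncorrected.

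The second reply is that there are safeguards. Recorded returns are subtracted, as in ordinary pill-count accounting. The schedule places a compliance check at the end-of-treatment visit. Protocol 6.4 requires records of drug dispensed and used, and reconciliation of all drug at study completion. Separate administration and accountability listings (16.2.5.1 and 16.2.5.2) let a reader trace an odd value. All of this stands and may make missing counts rare, but it does not make the rule right when a count is missing.

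A reader might also infer three stronger points that the documents do not support:

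- That reported values will often exceed 100%. No dispensing, return or missingness figures are given, and with split counts and known returns a fully adherent subject scores exactly 100%.
- That all error in reported compliance is upward. A missing dispensed count can leave the total undefined or too low. Separately, the fixed 400 mg denominator lowers compliance after a dose reduction: full adherence at 300 mg shows 300/400 = 75%.
- That early stoppers are the subjects most likely to have unreturned bottles, because the end-of-treatment and safety follow-up visits may be combined. The provision for combining visits says nothing about tablet returns, and nothing says it cancels the compliance check.

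**Conclusion.** Both rules are wrong as written, and the correction is cheap.

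The formula overstates dose by a factor of 1.5 to 3 if taken literally, and by nothing if it was programmed by strength, which is the more plausible case. The zero-return rule overstates dose received, daily dose and compliance for any period with a missing return count, unless every dispensed tablet was in fact taken. It can push compliance above 100% even with correct strengths. The 107%, 121%, 143% and 200% figures are illustrations that rest on whole-bottle dispensing of 200 mg tablets and a missing return; they are not estimates of what happened in this trial. How often the rule was used cannot be determined from the documents.

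The reach is limited to descriptive exposure and compliance outputs. The primary endpoint and the decision rule do not use tablet counts, and duration of exposure is calculated from dosing dates and held days.

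**What to change.** In SAP 3.3.9:

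1. Define total dose as (100 mg tablets dispensed − 100 mg tablets returned) × 100 + (200 mg tablets dispensed − 200 mg tablets returned) × 200.
2. Delete the zero-return rule. When either count is missing for a period, use the doses recorded as actually taken on the Study Drug Administration CRF, if it captures them. Otherwise set dose and compliance for that period to missing, and exclude the period from both numerator and denominator.
3. Footnote Table 14.1.6 and Listing 16.2.5.3 with the number of subjects affected. If the sponsor wants the zero-return version, show it only as a sensitivity display.

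Dose level multiplied by days not held is not an adequate substitute in item 2. The SAP cites that CRF only for held days, and at 400 mg this product equals the compliance denominator, so the period would score 100% by construction.

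The cost is a few lines of SAP text and programming. Some values will become missing, and reported compliance may be lower.
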